| | | 4hr post dose | X ^e | X | | | | | | | |
| Cycle 25 | Day 1 | predose ^{a,b} | | X | X | X | X | | | | |
| Q8 cycles^o | Day 1 | predose ^{a,b} | | | | X | X | | | | |
| Q16 cycles^o | Day 1 | predose ^{a,b} | | X | X | | | | | | |
| At CR^o | | | | | X | | | | X ⁱ | | |
| At progression ^k | | | | X | X | | | X ^o | X ^o | | |
| EOT | | | X ^{f,o} | X ^f | | X ^{m,o} | X ^{m,o} | | | | |
| FU 1 (100 days after last dose of nivolumab) | | | | | | X ^o | X ^o | | | | |
| FU | | | | X (to be repeated Q6m starting at FU3) ^{n,o} | | | | | | | |

ADA=anti-drug antibodies; CR=complete response; EOT=End of Treatment; FNA=fine needle aspirate; FU=Followup; PD=pharmacodynamic; PK=pharmacokinetic

- a. Predose samples should be taken just prior to the administration (preferably within 30 minutes, however predose collection up to 4 hours before study drug administration would be acceptable). If the infusion is delayed and a predose sample was already collected, there is no need to collect an additional predose sample.
- b. When both study drugs are given, predose samples should be obtained prior to administration of any study drug.
- c. Required for Cohort B1 and B2 only.
- d. Cohorts A1, A2, B3, and B4 that did not have an ibrutinib run-in.
- e. If not done in Cycle 13, postdose samples for ibrutinib PK can be collected at a subsequent cycle.
- f. If possible, the EOT sample should be obtained within 48 hours after last intake of ibrutinib.
- g. Submission of tumor tissue from a biopsy performed during screening is mandatory (diagnostic block or slides), archival tissue is acceptable if fresh biopsy is not available.
- h. Extent of disease involvement in the bone marrow must be documented at screening based on the results of a bone marrow biopsy/aspirate performed within 90 days prior to enrollment or a bone marrow biopsy/aspirate performed during the screening period. If bone marrow biopsy/aspirate is performed during screening (after obtaining informed consent), submission of bone marrow aspirate is encouraged.
- i. If the bone marrow was involved by lymphoma at baseline, a bone marrow biopsy and/or aspirate will be required to confirm a CR. Submission of bone marrow aspirate to the central lab is required if clinically feasible.
- j. Subjects are required to undergo tumor and/or bone marrow biopsies from C13 onwards if clinically indicated. When tumor biopsy is performed, submission of tumor biopsy to the central lab is required if clinically feasible.
- k. Samples, including fresh biopsy upon progression, are to be taken \pm 7 days at the discretion of the investigator.
- l. Applicable to Part B : Only required for subjects (as clinically indicated) in Cohort B1 (mandatory), B2 (mandatory), and optional for B3 and B4. C3D1 timepoint can be taken from C2D1 onwards.
- m. Sampling at clinical visit End-of-treatment per T&E [Table 1](#) (approx. 30 days post Ibrutinib dose).
- n. During FU to be repeated until progressive disease.
- o. After clinical cutoff: Assessment is no longer required.
- p. Pharmacokinetic, pharmacodynamic or biomarker samples will not be obtained at any visit, including follow up, after implementation of protocol amendment 7.

ABBREVIATIONS

| | |
|------------------|---|
| ADA | anti-drug antibody |
| AE | adverse event |
| AESI | adverse events of special interest |
| ALC | absolute lymphocyte count |
| ALT | alanine aminotransferase |
| ANC | absolute neutrophil count |
| AST | aspartate aminotransferase |
| AUC | area under the plasma concentration versus time curve |
| BCR | B-cell receptor |
| BM | bone marrow |
| B-NHL | B-cell non-Hodgkin lymphoma |
| BTK | Bruton's tyrosine kinase |
| CI | confidence interval |
| CLL | chronic lymphocytic leukemia |
| CR | complete response |
| C _{max} | maximum observed plasma concentration |
| CMV | cytomegalovirus |
| CT | computed tomography |
| CV | coefficient of variation |
| DILI | drug-induced-liver-injuries |
| DLBCL | diffuse large B-cell lymphoma |
| DLT | dose-limiting toxicity |
| ECG | electrocardiogram |
| ECOG | Eastern Cooperative Oncology Group |
| eCRF | electronic case report form |
| eDC | electronic data capture |
| EI | equivalence interval |
| EOT | end of treatment |
| ERK | extracellular signal-regulated kinase |
| FISH | fluorescence in situ hybridization |
| FL | follicular cell lymphoma |
| FU1 | follow up 1 |
| GCB | germinal-center –B-cell like |
| GCP | Good Clinical Practice |
| GFR | glomerular filtration rate |
| HER | human epidermal growth factor receptor |
| HIV | human immunodeficiency virus |
| ICF | informed consent form |
| ICH | International Conference on Harmonisation |
| IEC | Independent Ethics Committee |
| IFN γ | interferon gamma |
| IHC | immunohistochemistry |
| IL-2 | interleukin 2 |
| irAE | immune-related adverse event |
| INR | international normalized ratio |
| IRB | Institutional Review Board |
| ITK | interleukin-2-inducible T-cell kinase |
| ITSM | distal immunoreceptor tyrosine-based switch motif |
| IV | intravenous |
| IWCLL | International Workshop on Chronic Lymphocytic Leukemia |
| IWRS | interactive web response system |
| LC-MS/MS | liquid chromatography/mass spectrometry/mass spectrometry |
| LDT | lymphocyte doubling time |
| LFT | liver function test |
| mAb | monoclonal antibody |

| | |
|-----------|--|
| MCL | mantle cell lymphoma |
| MDRD | Modified Diet in Renal Disease (formula) |
| MedDRA | Medical Dictionary for Regulatory Activities |
| MLR | mixed lymphocyte reaction |
| MM | multiple myeloma |
| MRI | magnetic resonance imaging |
| MTD | maximum tolerated dose |
| mTPI | Modified Toxicity Probability Interval |
| NCI-CTCAE | National Cancer Institute Common Terminology Criteria for Adverse Events |
| NHL | non-Hodgkin's lymphoma |
| NSAIDs | nonsteroidal anti-inflammatory drugs |
| NSCLC | non-small-cell lung cancer |
| ORR | overall response rate |
| PD | pharmacodynamic |
| PD-1 | programmed-cell death 1 |
| PET | positron emission tomography |
| PFS | progression-free survival |
| PK | pharmacokinetics |
| PQC | Product Quality Complaint |
| PR | partial response |
| PRL | partial response with lymphocytosis |
| QTcF | QT interval corrected for heart rate, using Fridericia formula |
| RCC | renal-cell cancer |
| RP2D | recommended phase 2 dose |
| SET | Study Evaluation Team |
| SIPPM | Site Investigational Product Procedures Manual |
| SJS | Stevens-Johnson Syndrome |
| SLL | small lymphocytic lymphoma |
| TCR | T-cell receptor |
| Th2 | T-helper type 2 |
| ULN | upper limit of normal |
| WHO | World Health Organization |
| WM | Waldenström's macroglobulinemia |
| WOCBP | women of childbearing potential |

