| 
Treatment Period begins with the first administration of study therapy. EOT visit is required for all subjects and should take place within 30 days after last dose of study therapy with a window of ±7 days. If the subject requires subsequent anti-lymphoma/neoplastic therapy in the interim period between last dose of study drug and the EOT visit, then this visit should be completed just prior to initiation of subsequent therapy. Follow-up visits in all subjects will be completed every 3 months with a window of ±7 days until death or end of study. Note that the first FU visit should be approximately 100 days after end of nivolumab therapy; during this first FU visit, additional sampling will be done.
 
After the clinical cutoff, subjects who are ongoing on treatment continue all assessment per protocol, however data collected on eCRF will be limited to at least: SAEs and AEs Grade ≥3, laboratory assessments (Grade ≥3 or clinically significant), efficacy assessments, survival status, and study treatment administration.
 
Per Amendment 7, subjects who are receiving study treatment will continue all assessments per protocol. Data collected in the eCRF will be further limited to: SAEs and Grade ≥3 AEs that are at least possibly related to treatment, AEs leading to discontinuation or modification, efficacy assessments, and study treatment administration.
 | | | | | | |
| Weight/Height | Height at Screening only. | X | X | X | X | |
| 12-lead ECG | Assessment of triplicate ECG to determine QTcF; repeat ECG 3 times approximately 1-2 minutes apart. Predose Baseline= prior to any study treatment Predose C2D1=within 1 hour prior to nivolumab dosing | X | •Predose •Immediately after nivolumab infusion on C1D1 •2 hours after ibrutinib dosing on C1D1 | •Cycle 2 Day1: predose •Cycle 5 Day 1: after end of nivolumab infusion •To be repeated as clinically indicated | X | |
| Concomitant Medications | Collect up to EOT (within 30 days after the last dose of ibrutinib or whichever treatment occurred last). Thereafter, collect only subsequent anti-lymphoma/neoplastic therapy. | <-----X-----> | | | | |
| Adverse Events | Record all AEs from signing of ICF to EOT (within 30 days after the last dose of ibrutinib or nivolumab, whichever treatment occurred last). | <-----X-----> | | | | |
| Laboratory Assessments | | | | | | |

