- subject refuses further therapy
- investigator's decision to withdraw the subject
- pregnancy of the subject
- noncompliance with study treatment or procedure requirements

The average duration of study therapy is expected to be approximately 6 months.

In Part A of the study, a SET, consisting of the principal investigators, sponsor medical monitors, and the sponsor's clinical pharmacologist, or their designees, and the sponsor statistician will review all available data upon completion of the first 2 treatment cycles (ie, 4 weeks of study therapy) for all subjects at each dose cohort to determine DLTs, if dose escalation is acceptable, and ultimately to determine the recommended Phase 2 dose.

In Part B of the study, all subjects in each cohort may be evaluated for response by the SET and additional functional representatives from Janssen, as applicable. The SET along with optional other internal members may review safety on an ad hoc basis, and efficacy endpoints (including but not limited to ORR).

The End-of-Treatment Visit will occur within 30 days after the last dose of ibrutinib or nivolumab, whichever treatment occurred last.

During the Follow-up Period, long-term safety, survival status, disease progression, subsequent anticancer therapy, and occurrence of other primary malignancy data will be collected as well as anti-drug antibody (ADA) sampling if applicable. During the Follow-up Period, subjects should be followed for safety up to 30 days after the last dose of ibrutinib or 100 days after the last nivolumab infusion, whichever is later. The safety follow-up includes adverse event reporting and laboratory assessments (at the first follow-up). Thereafter, follow-up visits will be completed approximately every 3 months until death or the end of study. Subjects who have developed treatment-related Grade 3 or higher toxicity at the end of treatment will be assessed until recovery to Grade ≤ 1 or baseline, deemed irreversible, or until end of study. Adverse events leading to

discontinuation will be followed up until resolution or return to baseline, or end of study, whichever occur first.

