9. CONCOMITANT THERAPY

Concomitant medications and any medications used to treat or support AEs will be collected in the eCRF and recorded in the source documents throughout the study beginning with signing of informed consent form to 30 days after the last dose of ibrutinib, 100 days after the last dose of nivolumab, or, afterwards, during the follow-up of a related SAE (if applicable). Otherwise, in Follow-up Period, only subsequent anti-lymphoma/neoplastic therapy should be documented (see Section 9.5). The sponsor must be notified in advance (or as soon as possible thereafter) of any instances in which prohibited therapies are administered (eg, CYP3A inhibitors, vitamin K antagonists). All medications (prescriptions or over the counter medications) continued at the start of the study or started during the study and different from the study drug must be documented in the concomitant therapy section of the eCRF.

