13.3. Procedures

13.3.1. All Adverse Events

All adverse events and special reporting situations, whether serious or non-serious, will be reported from the time a signed and dated ICF is obtained until 30 days after the last dose of ibrutinib or 100 days after the last nivolumab infusion, whichever is later. Afterwards, report only SAEs that are at least possibly related to study treatment. After the clinical cutoff, only SAEs and Grade ≥ 3 AEs will be collected. Serious adverse events, including those spontaneously reported to the investigator within 30 days after the last dose of study therapy, must be reported using the Serious Adverse Event Form. The sponsor will evaluate any safety information that is spontaneously reported by an investigator beyond the time frame specified in the protocol.

Disease progression should not be recorded as an adverse event or serious adverse event term; instead, signs and symptoms of clinical sequelae resulting from disease progression/lack of efficacy will be reported if they fulfill the serious adverse event definition (refer to Section 13.1.1). Death should not be recorded as an adverse event or serious adverse event, but as the outcome of an adverse event. The event that resulted in the death should be reported as a serious adverse event.

All events that meet the definition of a serious adverse event will be reported as serious adverse events, regardless of whether they are protocol-specific assessments.

All adverse events, regardless of seriousness, severity, or presumed relationship to study drug, must be recorded using medical terminology in the source document and eCRF; reporting on eCRF after CCO (per amendment #6 and 7 further revisions apply per [Table 1](#)[collection of SAEs and Grade ≥ 3 AEs, AEs leading to discontinuation or modification, laboratory assessments {Grade ≥ 3 or clinically significant}]). Whenever possible, diagnoses should be given when signs and symptoms are due to a common etiology (eg, cough, runny nose, sneezing, sore throat, and head congestion should be reported as "upper respiratory infection"). Investigators must record in the eCRF their opinion concerning the relationship of the adverse event to study therapy. All measures required for adverse event management must be recorded in the source document and reported according to sponsor instructions.

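### The Table 1 note ends recording of all AEs at EOT, while Protocol 3.1 and 13.3.1 and the SAP 5.1 TEAE window run to as late as 100 days after the last nivolumab

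*Protocol*

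**What the plan says.** **Shorter window.** The Adverse Events note in Protocol Table 1 reads "Record all AEs from signing of ICF to EOT (within 30 days after the last dose of ibrutinib or nivolumab, whichever treatment occurred last". The header of the same table says that the EOT visit "should take place within 30 days after last dose of study therapy with a window of" 7 days either side, and that it is brought forward when new anti-lymphoma therapy is needed sooner. It lists a separate, later visit: "the first FU visit should be approximately 100 days after end of nivolumab therapy".

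**Longer window.** Protocol 3.1 has subjects "followed for safety up to 30 days after the last dose of ibrutinib or 100 days after the last nivolumab infusion", whichever is later, and adds: "The safety follow-up includes adverse event reporting and laboratory assessments". The synopsis says the same. Protocol 13.3.1 requires all AEs, serious or not, "until 30 days after the last dose of ibrutinib or 100 days after the last nivolumab infusion, whichever is later". Protocol 13.1.1 refers the reader to 13.3.1 for when AE recording stops.

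**Analysis.** SAP 5.1 counts TEAEs to the later of ibrutinib + 30 days and nivolumab + 100 days, or to the start of a subsequent systemic anticancer therapy if that comes first. It also counts treatment-related AEs whatever their start date.

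**Concomitant medications.** The Table 1 note reads "Collect up to EOT (within 30 days after the last dose of ibrutinib or whichever treatment occurred last", after which only anti-lymphoma or antineoplastic therapy is collected. Protocol 9 runs collection "to 30 days after the last dose of ibrutinib, 100 days after the last dose of nivolumab", or later during follow-up of a related SAE.

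**The concern.** The TEAE tables will be labelled with a window that reaches 100 days past the last nivolumab, but the note that sites see in the visit schedule asks for all AEs only to about day 30. Where a site followed the note, an event that was never recorded cannot enter the table. SAP 5.1's rule that related events count regardless of start date does not help, because it works only on recorded events.

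The events at risk are new, non-serious and mainly low-grade. The immune-related categories listed in SAP 5.3 include rash, pruritus, diarrhoea and changes in thyroid tests, which can be of that kind. The safety profile is a secondary objective, and the period that matters is before the clinical cutoff, when all AEs were meant to be collected. If some sites followed Table 1 and others 13.3.1, one incidence figure would mix two ascertainment periods.

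**Working it through.** There is no figure in the plan to reproduce. The check is a comparison of the two stopping rules, by date arithmetic.

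**Inputs**
- d = days that ibrutinib continues after the last nivolumab. If nivolumab is the last drug given, take d = 0.
- E = day of the EOT visit, counted from the last dose of either drug. Table 1 sets this at within 30 days, with 7 days either side. The latest is therefore 30 + 7 = day 37; there is no fixed earliest day.
- R = last day of all-AE reporting under 13.3.1, on the same count: R = max(30, 100 − d).

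**Gap = max(0, R − E).** At E = 30 this becomes max(0, 70 − d).

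| d (days) | E (day) | R (day) | Gap (days) |
|---|---|---|---|
| 0 | 30 | 100 | 100 − 30 = 70 |
| 0 | 37 | 100 | 100 − 37 = 63 |
| 14 | 30 | 86 | 86 − 30 = 56 |
| 42 | 30 | 58 | 58 − 30 = 28 |
| 70 or more | 30 | 30 | 0 |

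An EOT visit before day 30 lengthens the gap day for day. At d = 0 and E = 23, for example, it is 100 − 23 = 77. That is not a maximum, because 30 days is an upper limit on the visit and not its centre.

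**Which row is realistic.** Protocol 6.4 says a recommendation to discontinue applies to both drugs, with ibrutinib alone possible after consultation. So d near 0 is a realistic case, and large d is possible.

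**Subsequent therapy.** If EOT was brought forward because a new systemic therapy was starting, the general SAP 5.1 window closes when that therapy starts. EOT and the end of the TEAE window then nearly coincide, so the gap for that analysis is about zero. The gap against 13.3.1 remains, because that section has no such stop.

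**What stays covered.** 13.3.1 and 13.3.2 require SAEs independently of the Table 1 note. Protocol 13.2.1 puts Grade 3 or higher nivolumab events of clinical interest on the SAE reporting timelines. That probably covers them, though it could refer only to the speed of reporting. Protocol 3.1 follows AEs that led to discontinuation until they resolve, but those are existing events, not new onsets after EOT.

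**The case against.** The best reply is that the documents already say which rule governs. Protocol 13.1.1 points to 13.3.1; the synopsis, Protocol 3.1 and SAP 1.2 agree with it; and Table 1 itself schedules the visit at about 100 days, with serum chemistry. The note does not forbid recording after EOT. This makes it likely that some sites collected to day 100. It does not remove the conflict: Protocol 10.6 sends sites to Table 1 for the timing of safety assessments, Protocol 3.1 cites Table 1 as the full list of procedures, and nothing says that the text overrides the table.

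SAP 2.2 defines an end-of-treatment phase that reaches nivolumab + 100 days. That is an analysis phase and does not change the EOT visit in Table 1, which is defined at 30 days.

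Two further objections stand. After the clinical cutoff, and more so under Amendment 7, the eCRF no longer takes most of the low-grade AEs at issue, so editing the note has little forward effect. And no stated SAP result depends on the concomitant-medication mismatch: SAP 3.6 sets no post-treatment window, and Protocol 9 has no wording to take the later of its dates. That part is a wording point only. So is Protocol 12.2, which limits AE analysis to onset in the Treatment Period, because Protocol 12 leaves the detail to the SAP.

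A reader might infer that late serious toxicity was missed, or that the reported irAE rates are too low. The documents support neither. SAEs fall outside the conflict, and nothing shows which rule sites followed.

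**Conclusion.** The conflict is real, stands in current text, and should be reconciled. The nominal gap is max(0, 70 − d) days with EOT at day 30, and it varies with the EOT date and with subsequent therapy as worked above. The consequence is conditional: TEAE and irAE incidence before the cutoff may be understated, or uneven across sites, for new non-serious events between EOT and day 100 after nivolumab, if sites followed the note. It affects only subjects who stopped before the cutoff without early subsequent therapy or prolonged ibrutinib. The conclusion rests on the words of the note. The span of the arrow in that table row cannot be read in the text reviewed, and it is not relied on. The size of any bias cannot be computed from the documents.

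**What to change.** 1. Reconcile the Table 1 Adverse Events note with Protocol 13.3.1 and SAP 5.1, keeping the eCRF limits that apply after the clinical cutoff and under Amendment 7.
2. State in the report what AE data were collected between EOT and day 100 after nivolumab. For data already in hand this is the most useful step.
3. Only if collection was incomplete or varied by site, show TEAEs and irAEs to 30 days after the last dose beside the 100-day table.
4. As minor wording points, reconcile the Table 1 concomitant-medication note with Protocol 9, and the Protocol 12.2 onset window with SAP 5.1.

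Cost: two table notes, one phrase in Protocol 12.2 and one statement in the report. No SAP section needs changing and no visit is added, since the visit at about 100 days already exists. The second set of tables is needed only if step 2 shows a problem.

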1. INTRODUCTION

Ibrutinib, (IMBRUVICA®; PCI-32765; JNJ-54179060), is a first-in-class, orally administered, potent inhibitor of Bruton's tyrosine kinase (BTK), a mediator of critical B-cell signaling pathways implicated in the pathogenesis of B-cell cancers. Ibrutinib is currently being co-developed by Janssen Research & Development, LLC (JRD) and Pharmacyclics LLC. It has demonstrated single-agent activity and an acceptable safety profile in several B-cell lymphomas, including relapsed/refractory mantle cell lymphoma (MCL) and chronic lymphocytic leukemia (CLL). Ibrutinib and PCI-32765 refer to the same molecule; hereafter, ibrutinib will be used.

Ibrutinib is currently being evaluated in over 26 ongoing and 9 completed company-sponsored clinical studies in healthy volunteers and in subjects with recurrent B-cell lymphomas, including CLL/small lymphocytic lymphoma (SLL), MCL, follicular lymphoma (FL), diffuse large B-cell lymphoma (DLBCL), multiple myeloma (MM), Waldenström's macroglobulinemia (WM), and marginal zone lymphoma (MZL).

Nivolumab (BMS-936558) is a fully human, IgG4 (κ) isotype, monoclonal antibody (mAb) that binds PD-1. Blockade of the PD-1 pathway by nivolumab was studied using the mixed lymphocyte reaction (MLR). PD-1 blockade resulted in a reproducible enhancement of both proliferation and IFN- γ release in the MLR. The effect of nivolumab on antigen-specific recall response was investigated using a CMV-restimulation assay with human peripheral blood mononuclear cells (PBMCs), and was evaluated by ELISA. These data indicated that nivolumab, versus an isotype-matched control antibody, augmented IFN- γ secretion from CMV-specific memory T-cells in a dose-dependent manner. PD-1 blockade by nivolumab is therefore considered a promising immunotherapeutic option.

Relevant clinical and nonclinical information are discussed within this section. For the most comprehensive nonclinical and clinical information regarding the efficacy and safety of ibrutinib and nivolumab, refer to the latest version of the ibrutinib and nivolumab Investigator's Brochures, Addenda, and Supplements. The term "sponsor" used throughout this document refers to the entities listed in the Contact Information page(s), which will be provided as a separate document.

